8.1.1.1. Ancillary Supplies for Participant Use

Study sites will distribute Sponsor-provided oral thermometers and rulers for use by participants to assess body temperature and injection site reactions, respectively, for recording solicited ARs in the eDiaries. Based on availability, smartphone devices may be provided to those participants who do not have their own device to use for eDiary activities.

8.1.2. Safety Telephone Call

A safety telephone call is a telephone call made to the participant by a trained site personnel. This call will follow a Sponsor-approved script, which will facilitate the collection of relevant safety information. Safety calls by the site to each participant will occur at the time points indicated in the SoE (Table 1). The participant will be interviewed according to the script about the occurrence of AEs, MAAEs, AESIs, SAEs, AEs leading to discontinuation, concomitant medications associated with those events, and any non-study vaccinations (Section 8.4.9). In addition, study personnel will collect information on known participant exposure to someone with COVID-19 or SARS-CoV-2 infection and on the participant's experience of COVID-19 symptoms. All safety information collected from the telephone call must be documented in the source documents as described by the participant and not documented on the script used for the safety telephone contact. As noted in Section 8.1.1, an unscheduled follow-up safety call may be triggered if an eDiary record results in identification of a relevant safety event.

8.1.3. Pregnancy Testing

Pregnancy testing includes the following:

- A point-of-care urine pregnancy test will be performed at the Screening Visit and before the IM injections on Day 1. At any time, a pregnancy test either via blood or point-of-care urine can be performed, at the discretion of the investigator.
- If not documented in a female participant's medical records, FSH test may be performed at the Screening Visit, as necessary and at the discretion of the investigator, to confirm menopausal status (please see Section 11.2 for details).

8.1.4. Vital Sign Measurements

Vital sign measurements will include systolic and diastolic blood pressure, heart rate, respiratory rate, and body temperature (preferred route is oral). The participant will be seated for at least 5 minutes before all measurements are taken. Vital signs will be measured at the time points indicated in the SoE (Table 1). On the day of IP administration, vital sign measurements will be collected once before and at least 60 minutes after vaccination. Vital signs may be collected at other study visits in conjunction with a symptom-directed physical examination.

If any of the vital sign measurements meet the toxicity grading criteria for clinical abnormalities of Grade 3 or greater, the abnormal value and grade will be documented in the AE section of the eCRF (unless there is another known cause of the abnormality that would result in an AE classification). The investigator will continue to monitor the participant with additional assessments until the vital sign value has reached the reference range, returns to the vital sign value at baseline, or is considered stable or until the investigator determines that follow-up is no longer medically necessary.

Participants who are febrile (body temperature $\geq 38.0^{\circ}\text{C}/100.4^{\circ}\text{F}$) before injection on Day 1 may be rescheduled within the relevant window period to receive the injection. Afebrile participants with minor illnesses may be vaccinated at the discretion of the investigator.

When procedures overlap and are scheduled to occur at the same time point, the order of procedures should be vital sign measurements and then blood collection.

8.1.5. Safety Laboratory Assessments

Blood samples for safety testing will be taken at Screening and Day 8. Safety laboratory tests will include total white blood cell count, hemoglobin, platelets, ALT, AST, total bilirubin, alkaline phosphatase, and creatinine. Any clinically significant finding (DHHS 2007) identified on the safety laboratory testing should be reported as an AE.

Additional blood samples for safety laboratory tests may be taken at the discretion of the investigator if warranted to ensure participant's safety.

8.1.6. Physical Examinations

A full physical examination, including height and weight, will be performed at the Screening Visit as indicated in the SoE (Table 1). The full examination will include assessment of skin, head, ears, eyes, nose, throat, neck, thyroid, lungs, heart, cardiovascular system, abdomen, lymph nodes, and musculoskeletal system and extremities. At Screening, the BMI will be calculated using the formula weight (kg) / (height [m])². Any clinically significant finding identified during a study visit should be reported as an MAAE.

Symptom-directed physical examinations may be performed at other time points at the discretion of the investigator. On the day of vaccination, prior to injection, both arms and associated lymph nodes should be examined, and any abnormalities should be documented.

8.1.7. Electrocardiogram (ECG)

A 12-lead electrocardiogram (ECG) will be obtained, after 10 minutes of supine rest, at Visit 1/Day 1 prior to vaccination. Skin preparation should be thorough and electrode placement should be according to standard 12-lead ECG procedure. The purpose of the ECG is to serve as a baseline comparison, should it be necessary, for subsequent clinical evaluation of suspected myocarditis/pericarditis. The ECG output should be filed in the participant's binder. No additional action (including review/interpretation) is required.

8.1.8. Assessment for Respiratory Viral Infection

During the study, participants might experience symptoms consistent with ILI or SARS-CoV-2 infection.

All participants will provide NP swab samples before the injection on Day 1 for assessment of infection with respiratory pathogens, including influenza viruses and SARS-CoV-2, as influenza or COVID-19 symptoms may confound reactogenicity assessments (CDC 2021b).

A study illness visit or a consultation will be arranged within 24 hours or as soon as possible to collect an NP swab (Table 1) to test for presence of respiratory pathogens (including influenza viruses and SARS-CoV-2) via RT-PCR if a participant experiences:

• Symptoms of ILI or SARS-CoV-2 infection (for definitions, see Section 8.4.5 and Section 8.4.6).

Additionally, clinical information will be carefully collected to evaluate the severity of the clinical case. All findings will be recorded in the eCRF.

• Participants will be instructed to report via Symptom Reporting eDiary or telephone calls whether ILI/COVID-19 symptoms have been experienced (see Section 8.4.5 and Section 8.4.6 for symptoms), once weekly from Day 1 through Day 181/EoS. If symptoms occur, participants will be directed to return to the study site as soon as possible, but no later than 72 hours after the onset of symptoms, for medical evaluation and an NP swab. Participants will be contacted by the study site if they have missed reporting in the eDiary. If there is no response to an eDiary prompt for 2 consecutive entries, the study site staff will contact the study participant by telephone.

It is important to note that some of the symptoms of ILI and COVID-19 overlap with solicited systemic ARs that are expected after vaccination with mRNA-1073, mRNA-1010, and mRNA-1273 (eg, myalgia, headache, fever, and chills). During the first 7 days after vaccination, when these solicited ARs are common, investigators should use their clinical judgment to decide whether an NP swab should be collected. The collection of an NP swab prior to the Day 1 vaccination can help ensure that cases of influenza or COVID-19 are not overlooked. Any study participant reporting symptoms consistent with protocol-defined ILI (Section 8.4.5) or COVID-19 (Section 8.4.6) during the 7-day period after vaccination should be evaluated for COVID-19 and influenza.

If scheduled, a study site illness visit may include additional assessments such as medical history and physical examination. The NP swab sample may be tested by multiplex RT-PCR for respiratory viruses besides SARS-CoV-2 and influenza to evaluate the severity of the clinical case.

All cases that meet the CDC definition of ILI and/or COVID-19 will be captured as MAAEs, along with relevant concomitant medications and details about severity, seriousness, and outcome.

8.2. Immunogenicity Assessments

Blood samples for immunogenicity assessments will be collected at the time points indicated in the SoE (Table 1). Immunogenicity assessments will be performed for all participants. Immune response to influenza vaccine antigens will be using HAI assay, with potential utilization on microneutralization assay for influenza strains that do not perform favorably in the HAI assay. Immune responses to SARS-CoV-2 vaccine antigens will utilize either pseudovirus neutralization (PsVNA) nAb assay or multiplex bAb assay, depending on the timing of data delivery. The following analytes will be measured:

• Influenza: Serum antibody level as measured by HAI assay

- Influenza: Serum nAb level as measured by microneutralization assay as potential substitution to the HAI assay
- SARS-CoV-2: Serum nAb titers as measured by PsVNA and potentially serum binding antibody titers by ELISA or multiplex assay specific to the SARS-CoV-2 proteins
- Cellular immunogenicity in a subset of participants

Sample aliquots will be designed to ensure that backup samples are available and that vial volumes are likely to be adequate for future testing needs. The actual date and time of each sample will be collected. Unique sample identification will be utilized to maintain the blind at the laboratory at all times and to allow for automated sample tracking and housing. Handling and preparation of the samples for analysis, as well as shipping and storage requirements, will be provided in a separate study manual.

Measurement of antibody levels will be performed in a laboratory designated by the Sponsor.

According to the ICF (Section 11.1.6), excess serum from immunogenicity testing may be used for future research, which may be performed at the discretion of the Sponsor to further characterize the immune response to influenza and SARS-CoV-2 viruses, additional assay development, and the immune response across influenza viruses.

8.3. Efficacy Assessments

While the study will not be powered for efficacy assessments, symptoms of infection with respiratory pathogens will be tracked as an exploratory objective in this study.

8.4. Safety Definitions and Related Procedures

8.4.1. Adverse Event

An AE is defined as any untoward medical occurrence associated with the use of a drug/vaccine in humans, whether or not considered related to the drug/vaccine.

Events Meeting the Adverse Event Definition

- Exacerbation of a chronic or intermittent pre-existing condition including an increase in frequency and/or intensity of the condition, after the IP injection.
- New conditions detected or diagnosed after the IP injection even though they may have been present before the start of the study.

Events NOT Meeting the Adverse Event Definition

• Procedures planned before study entry (eg, hospitalization for preplanned surgical procedure).

- Medical or surgical procedure (eg, endoscopy, appendectomy): the condition that leads to the procedure should be the AE.
- Situations in which an untoward medical occurrence did not occur (social and/or convenience admission to a hospital).

An AR is any AE for which there is a reasonable possibility that the vaccine caused the AE (Section 8.4.3). For the purposes of IND safety reporting, "reasonable possibility" means that there is evidence to suggest a causal relationship between the vaccine and the AE.

An unsolicited AE is any AE reported by the participant that is not specified as a solicited AR in the protocol or is specified as a solicited AR but starts outside the protocol-defined period for reporting solicited ARs (ie, 7 days after vaccination).

An incidental, asymptomatic RT-PCR confirmed COVID-19 case (ie, workplace screening) should be reported as an unsolicited AE of "asymptomatic COVID-19" if occurring during the first 28 days post study vaccination unless the RT-PCR test was performed on the NP swab collected prior to study vaccination (Day 1).

8.4.2. Serious Adverse Events

An AE (including an AR) is considered an SAE if, in the view of either the investigator or Sponsor, it results in any of the following outcomes:

Death

A death that occurs during the study or that comes to the attention of the investigator during the protocol-defined follow-up period must be reported to the Sponsor, whether or not it is considered related to the IP.

• Is life-threatening

An AE is considered life-threatening if, in the view of either the investigator or the Sponsor, its occurrence places the participant at immediate risk of death. It does not include an AE that, had it occurred in a more severe form, might have caused death.

• Inpatient hospitalization or prolongation of existing hospitalization

In general, inpatient hospitalization indicates the participant was admitted to the hospital or emergency ward for at least one overnight stay for observation and/or treatment that would not have been appropriate in the physician's office or outpatient setting. The hospital or emergency ward admission should be considered an SAE regardless of whether opinions differ as to the necessity of the admission. Complications that occur during inpatient hospitalization will be recorded as AEs; however, if a complication/AE prolongs hospitalization or otherwise fulfills SAE criteria, the complication/AE will be

recorded as a separate SAE. Procedures planned before study entry (eg, hospitalization for preplanned surgical procedure) are not considered SAEs.

• Persistent or significant incapacity or substantial disruption of the ability to conduct normal life functions

This definition is not intended to include experiences of relatively minor medical significance such as uncomplicated headache, nausea/vomiting, diarrhea, influenza, and accidental trauma (eg, sprained ankle) which may interfere with or prevent everyday life functions but do not constitute a substantial disruption.

• Congenital anomaly or birth defect

• Medically important event

Medical judgment should be exercised in deciding whether SAE reporting is appropriate in other situations, such as important medical events that may not be immediately life-threatening or result in death or hospitalization but may jeopardize the participant or require medical or surgical intervention to prevent one of the other outcomes listed in the above definition. These events should usually be considered serious. Examples of such medical events include allergic bronchospasm requiring intensive treatment in an emergency room or at home, blood dyscrasias or convulsions that do not result in inpatient hospitalization, or the development of drug dependency or drug abuse.

8.4.3. Solicited Adverse Reactions

The term "reactogenicity" refers to the occurrence and intensity of selected signs and symptoms (ARs) occurring after IP injection. The eDiary will solicit daily participant reporting of ARs using a structured checklist (Section 8.1.1). Participants will record such occurrences in an eDiary during the 7 days after vaccination (ie, the day of injection [Day 1] and 6 subsequent days). Local solicited ARs will be recorded separately for each injection site.

Severity grading of reactogenicity will occur automatically based on participant entry into the eDiary according to the grading scales presented in Table 6 modified from the Toxicity Grading Scale for Healthy Adult and Adolescent Volunteers Enrolled in Preventive Vaccine Clinical Trials (DHHS 2007).

If a participant reported a solicited AR during the solicited period and did not record the event in the eDiary, the event should be recorded on the Reactogenicity page of the eCRF. If the event starts during the solicited period, but continues beyond 7 days after dosing, the site should collect an end date from the participant to close out the event on the Reactogenicity page of the eCRF. If the participant reported an event after the solicited period (ie, after Day 7), it should be recorded as an AE on the AE page of the eCRF.

All solicited ARs (local and systemic) will be considered causally related to dosing.

 Table 6
 Solicited Adverse Reactions and Grades

Reaction	Grade 1	Grade 2	Grade 3	Grade 4
Injection site pain	No interference with activity	Some interference with activity	Prevents daily activity	Requires emergency room visit or hospitalization
Injection site erythema (redness)	25-50 mm/ 2.5-5 cm	51-100 mm/ 5.1-10 cm	> 100 mm/ > 10 cm	Necrosis or exfoliative dermatitis
Injection site swelling/induration (hardness)	25-50 mm/ 2.5-5 cm	51-100 mm/ 5.1-10 cm	> 100 mm/ > 10 cm	Necrosis
Axillary (underarm) swelling or tenderness ipsilateral to the side of injection	No interference with activity	Some interference with activity	Prevents daily activity	Emergency room visit or hospitalization
Headache	No interference with activity	Some interference with activity	Prevents daily activity	Requires emergency room visit or hospitalization
Fatigue	No interference with activity	Some interference with activity	Significant; prevents daily activity	Requires emergency room visit or hospitalization
Myalgia (muscle aches all over body)	No interference with activity	Some interference with activity	Significant; prevents daily activity	Requires emergency room visit or hospitalization
Arthralgia (joint aches in several joints)	No interference with activity	Some interference with activity	Significant; prevents daily activity	Requires emergency room visit or hospitalization

Reaction	Grade 1	Grade 2	Grade 3	Grade 4
Nausea/vomiting	No interference with activity or 1-2 episodes/ 24 hours	Some interference with activity or > 2 episodes/24 hours	Prevents daily activity, requires outpatient intravenous hydration	Requires emergency room visit or hospitalization for hypotensive shock
Chills	No interference with activity	Some interference with activity not requiring medical intervention	Prevents daily activity and requires medical intervention	Requires emergency room visit or hospitalization
Fever (oral)	38.0-38.4°C 100.4-101.1°F	38.5-38.9°C 101.2-102.0°F	39.0-40.0°C 102.1-104.0°F	> 40.0°C > 104.0°F

Abbreviations: AE = adverse event; eCRF = electronic case report form.

Note: Events listed above but starting > 7 days post study injection will be recorded on the AE page of the eCRF. Causality for each event will be determined per assessment by the Investigator.

Source: Modified from DHHS 2007.

Any solicited AR that meets any of the following criteria must be entered into the participant's source document and must also be recorded by the study site staff on the reactogenicity page of the participant's eCRF:

- Solicited local or systemic AR that results in a visit to a healthcare practitioner (HCP), to be recorded as an MAAE (Section 8.4.4).
- Solicited local or systemic AR leading to the participant withdrawing from the study or the participant being withdrawn from the study by the investigator (AE leading to withdrawal).
- Solicited local or systemic AR lasting beyond 7 days post injection.
- Solicited local or systemic AR that otherwise meets the definition of an SAE.

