8.4.6. Suspicion of SARS-CoV-2 Infection

SARS-CoV-2 should be suspected if the participant experiences the acute onset or worsening of any one of the symptoms listed below (CDC 2021c):

- Fever (temperature ≥ 38.0 °C [100.4°F]) or chills (of any duration)
- Cough (of any duration)
- Shortness of breath and/or difficulty breathing (of any duration)
- Nausea, vomiting or diarrhea (of any duration)
- Fatigue (lasting \geq 48 hours)
- Muscle or body aches (lasting \geq 48 hours)
- Headache (lasting \geq 48 hours)
- New loss of taste and/or smell (lasting \geq 48 hours)
- Sore throat, congestion, or runny nose (lasting ≥ 48 hours)

Symptomatic COVID-19 is defined by the presence of one of the above CDC-listed symptoms (CDC 2021c) and a positive RT-PCR test on a respiratory sample. Asymptomatic SARS-CoV-2

infection is defined as a positive RT-PCR test on a respiratory sample in the absence of symptoms or a positive serologic test for anti-nucleocapsid antibody after a negative test result at the time of enrollment, with the serologic assay detecting previously resolved SARS-CoV-2 infections that may have occurred between visits, and the RT-PCR to detect active viral infection at the time of a visit. If participants are confirmed to have SARS-CoV-2 infection and are symptomatic or asymptomatic, the investigator will notify the participants' primary care physicians of the diagnosis and the local public health authorities as required per local regulations.

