9.4. Analysis Sets

The analysis sets are described in Table 8.

Table 8 Analysis Sets

Set	Description	
Randomization Set	The randomization set consists of all participants who are randomly assigned.	
FAS ¹	The FAS consists of all randomly assigned participants who receive the IP.	
PP Set ²	The PP set consists of all participants in the FAS who comply with the injection schedule, comply with the timings of immunogenicity blood sampling to have a baseline and at least 1 post-injection assessment, do not have influenza or SARS-CoV-2 infection at baseline and post-baseline up to Day 29 (as documented by positive RT-PCR testing result), and have no major protocol deviations and/or prohibited concomitant medication use (documented in the Section 6.5.3) that are prespecified with impacts on the immune response and should be excluded from the PP set.	
Safety Set ³	The safety set consists of all randomly assigned participants who receive the IP.	

Set	Description	
Solicited Safety Set ⁴	The solicited safety set consists of all participants in the safety set who contribute any solicited AR data.	

Abbreviations: AR = adverse reaction; FAS = full analysis set; IP = investigational product; PP = per-protocol.

- ¹ For the FAS, participants will be analyzed according to the group to which they were randomized.
- ² The PP set will be used as the primary analysis set for analyses of immunogenicity unless otherwise specified. Participants will be analyzed according to the group to which they were randomized.
- ³ The safety set will be used for all analyses of safety, except for the solicited ARs. Participants will be included in the vaccination group corresponding to what they actually received.
- ⁴ The solicited safety set will be used for the analyses of solicited ARs and participants will be included in the vaccination group corresponding to what they actually received.

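### The pre-dose Day 1 swab is justified by confounding of reactogenicity, yet no reactogenicity rule uses its result, and Section 8.4.6 lets a pre-dose positive followed by a vaccine reaction count as symptomatic COVID-19

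*Protocol*

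**What the plan says.** **Purpose of the swab.** The Synopsis (Assessment for Respiratory Viral Infection), Section 4.2 and Section 8.1.8 all give the same reason for swabbing every participant before injection: "as influenza or COVID-19 symptoms may confound reactogenicity assessments". Section 8.1.8 also acknowledges that myalgia, headache, fever and chills belong both to infection and to the expected vaccine reactions.

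**Reactogenicity rules.** Section 8.4.3 grades solicited reactions automatically from the diary and states "All solicited ARs (local and systemic) will be considered causally related to dosing". On who is analyzed, Section 9.4 says "The solicited safety set consists of all participants in the safety set who contribute any solicited AR data". Section 9.5.2 adds no split or flag by swab result.

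**Case definitions.** In Section 8.4.6, "Symptomatic COVID-19 is defined by the presence of one of the above CDC-listed symptoms", together with a positive RT-PCR on a respiratory specimen. Fever, chills, nausea and vomiting count at any duration; fatigue, aches and headache must last at least 48 hours. No interval between symptom and test is given. Section 8.4.5, by contrast, requires the influenza RT-PCR within 7 days of the onset of a protocol-defined ILI. Sections 4.1 and 8.4.4 make confirmed symptomatic COVID-19 an MAAE, unless it is an SAE.

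**Swabbing in the first 7 days.** Section 8.1.8 says that "investigators should use their clinical judgment to decide whether an NP swab should be collected". A few lines later it says that anyone reporting protocol-defined ILI or COVID-19 symptoms "during the 7-day period after vaccination should be evaluated for COVID-19 and influenza".

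**The concern.** A measurement is taken for a stated analytic reason, and the part of the plan that the reason concerns makes no use of it. Two errors of opposite direction follow.

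- **Infection counted as reaction.** A participant who is RT-PCR positive before dosing and has fever or myalgia from that infection in the diary week enters the solicited tables as a vaccine reaction. Solicited reactogenicity is a primary endpoint.
- **Reaction counted as infection.** A participant who is silently positive on the pre-dose swab and has vaccine chills on Day 2 has one listed symptom and a positive RT-PCR. Read literally, Section 8.4.6 makes this symptomatic COVID-19, and the MAAE rule follows. The same chills are also counted as a related solicited reaction.

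At stake are the absolute rates of less common systemic reactions in arms of 50 or 100, the exploratory count of COVID-19 cases and, to a lesser degree, the MAAE count. The two statements in 8.1.8 add a risk that sites differ in how often they swab during the diary week.

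**Working it through.** **1. Where the pre-dose result is used.**

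| Place | Use of the result | Bears on reactogenicity? |
|---|---|---|
| 9.4, PP set | Infection at baseline or up to Day 29 excludes the participant | No, the set serves immunogenicity |
| 8.4.1 | A positive on the pre-dose swab is not reported as an asymptomatic COVID-19 AE | No |
| 8.4.3, 9.4 (Solicited Safety Set), 9.5.2 | None | This is where the stated purpose lies |
| 8.4.6 | None; a pre-dose positive is not set apart | No, but it decides case status |
| 7.1.1 and 7.1.2, pause rules 2 and 6 | None named; another cause may be considered | Governs pausing, not the endpoint |

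The investigator-causality note under Table 6 covers only events starting more than 7 days after injection.

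**2. Overlap of the two symptom lists.** The solicited systemic reactions in Table 6 are headache, fatigue, myalgia, arthralgia, nausea/vomiting, chills and fever. All except arthralgia are in the 8.4.6 list, three of them (headache, fatigue, aches) only at 48 hours or more. Influenza is better protected: a protocol-defined ILI needs at least one respiratory symptom, which solicited reactions do not supply.

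**3. The plan's own figures.** Table 7 gives the only computed figures, from 1 − (1 − p)^n. They reproduce: 92.3% (n = 50, p = 5%), 78.2% (50, 3%), 95.2% (100, 3%) and 86.7% (100, 2%). They are not inputs here, but the same formula gives the chance that an arm of 100 has at least one pre-dose positive: 63.4% at an assumed positivity of 1%, 95.2% at 3% and 99.4% at 5%.

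**4. Infection counted as reaction.** All inputs are assumptions, because the documents give none of them:
- q, share RT-PCR positive before dosing: 1% to 5%, or 5.5 to 27.5 of 550
- s, share of positives with a solicited systemic symptom from the infection: 30% to 70%
- r, true rate of any vaccine-caused systemic reaction: 10% to 50%

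If infection symptoms and vaccine reactions are independent, the observed rate is r + (1 − r)·q·s, so the excess is (1 − r)·q·s.
- Lowest: (1 − 0.5) × 0.01 × 0.3 = 0.0015, or 0.15 percentage points
- Middle: (1 − 0.1) × 0.03 × 0.7 = 0.0189, or 1.89 percentage points
- Highest: (1 − 0.1) × 0.05 × 0.7 = 0.0315, or 3.15 percentage points

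One participant moves a rate by 1 point in an arm of 100 and by 2 points in Group 1 (n = 50).

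**5. Reaction counted as infection.** The expected number of pre-dose positives who also have a vaccine systemic reaction is 550·q·r.
- Lowest: 550 × 0.01 × 0.1 = 0.55
- Highest: 550 × 0.05 × 0.5 = 13.75

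This is generous for any given q and r. It treats every positive as free of infection symptoms and every reaction as meeting the list, although arthralgia does not and three reactions need 48 hours.

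**6. Would a time window alone repair 8.4.6?** No. A Day 1 swab and chills on Day 2 are one day apart, inside a 7-day window. The window removes distant pairings of symptom and test. The pre-dose positive also has to be reported separately.

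**The case against.** Several arguments on the other side are sound.

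- **Counting every solicited event as related is a legitimate convention.** It is conservative, uniform and needs no case-by-case attribution. This stands: the sentence in 8.4.3 is not an error, and the main table should stay as it is.
- **A supportive table belongs in the SAP.** Section 9.5.2 leaves detail to the SAP, which is not at hand, so the absence of such a table is not by itself a fault. The case definition and the swab instructions, however, are fixed in the protocol, and an SAP table does not repair them.
- **Eligibility already removes the ill.** Exclusion 1, exclusions 13 and 14 and Section 7.2.1 reduce symptomatic infection at dosing and so lower s. They act on illness, known history and contact, not on the swab result. Silent positives remain, and they are the group that 8.4.6 misclassifies. The PP-set and 8.4.1 rules themselves presuppose that some dosed participants are positive on Day 1.
- **The arms are randomized and observer-blind, and the analyses descriptive.** Infection is balanced in expectation, so differences between arms are affected less than absolute rates.
- **The MAAE effect is partial.** A solicited reaction that leads to a healthcare visit is already an MAAE under 8.4.3.
- **Section 8.1.8 can be read coherently:** evaluate everyone, swab on judgment. That reading is possible, but the text does not state it.

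A reader might infer that the swab result is never used, that the primary reactogenicity endpoint is invalid, or that dose selection is distorted. The documents do not support this. The result has two stated uses, the main convention is acceptable, and no distortion between arms is shown. A reader might also compute that 2 to 5 infected per 100 inflate a 5% reaction by 40% to 100% (2/5 to 5/5). That is a ceiling on assumed inputs: every infected participant would need that particular symptom and would not otherwise have had it.

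**Conclusion.** The point holds in a limited form. The protocol gives confounding of reactogenicity as its reason for the pre-dose swab but states no reactogenicity rule that uses the result. As written, Section 8.4.6 classifies a pre-dose positive with a vaccine reaction as symptomatic COVID-19. The second part rests on the text alone and needs no assumption about rates. It is a possible misclassification, not a certain one, since it requires both a positive RT-PCR and an overlapping symptom.

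The size depends wholly on assumed values. With 1% to 5% positive before dosing, the rate of any systemic reaction rises by about 0.15 to 3 percentage points. Between about 0.6 and 14 of 550 participants could meet the COVID-19 definition through a vaccine reaction. The effect on common reactions is probably small. It matters mainly for uncommon ones, such as Grade 3 systemic events, and for the exploratory COVID-19 count, where a handful of cases may be a large share.

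**What to change.** 1. **Section 9.5.2.** Keep the full Solicited Safety Set table, with all solicited reactions treated as related. Beside it, add a supportive table of solicited systemic reactions (any, and Grade 3 or higher) without participants RT-PCR positive for influenza or SARS-CoV-2 on the pre-dose Day 1 swab. This conditions only on a baseline result. List positives from symptom-triggered swabs in Days 1 to 7 rather than removing them: those swabs are prompted by the symptoms being counted, so removal would select on a post-dose outcome. If the SAP already has such a table, a cross-reference is enough.
2. **Section 8.4.6, analysis definition.** Link symptom onset to the positive test in time, as 8.4.5 does. Report pre-dose Day 1 positives with later symptoms separately from post-vaccination cases. Section 8.4.1 already draws this line for asymptomatic infection. Separate reporting keeps genuine COVID-19 with onset after dosing visible.
3. **Section 8.1.8.** Reconcile the two statements on evaluation and swabbing in the first 7 days, so that sites follow one instruction.

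The cost is one extra table and a few sentences; no new data are collected. The downside is that the added table will differ from the main one by few participants, about 1 to 5 per arm of 100 under the assumed positivity, and should be read accordingly.
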